5.1.3 Exclusion Criteria

If an individual meets any of the following criteria, he or she is ineligible for this study:

- 1. Received COVID-19 vaccines other than Moderna and/or Pfizer-BioNTech in the past, inclusive of clinical trial COVID-19 vaccines.
- 2. Participation in research involving receipt of investigational products (drug/biologic/device) within 90 days prior to study vaccination.
- 3. Received influenza vaccination within 14 days prior to study vaccination.
- Received any vaccine ≤ 45 days prior to study vaccination, except for rabies, human papilloma virus (HPV), tetanus-diphtheria (Td), tetanus, diphtheria, and pertussis (TDaP/DTap), hepatitis B virus (HBV), and meningococcal vaccines which may be given as medically indicated.
- 5. Any known allergies to products contained in the investigational product.
- 6. Any history of anaphylaxis to any prior vaccine.
- 7. Autoimmune or immunodeficiency disease/condition (iatrogenic or congenital) requiring ongoing immunomodulatory therapy.

NOTE: Stable endocrine disorders (eg, thyroiditis, pancreatitis), including stable diabetes mellitus with no history of diabetic ketoacidosis) are NOT excluded.

8. Chronic administration (defined as > 14 continuous days) of immunosuppressant, systemic glucocorticoids, or other immune-modifying drugs within 90 days prior to study vaccination.

NOTE: An immunosuppressant dose of glucocorticoid is defined as a systemic dose ≥ 10 mg of prednisone per day or equivalent. The use of topical or intranasal glucocorticoids is permitted. Topical tacrolimus and ocular cyclosporin are permitted.

- 9. Received immunoglobulin, blood-derived products, or immunosuppressant drugs within 90 days prior to study vaccination, except for rabies immunoglobulin which may be given if medically indicated.
- 10. Active cancer (malignancy) on therapy within 3 years prior to study vaccination (with the exception of adequately treated non-melanomatous skin carcinoma or lentigo maligna and uterine cervical carcinoma in situ without evidence of disease, at the discretion of the investigator).
- 11. Participants who are breastfeeding, pregnant, or who plan to become pregnant prior to the end of study.

- 12. Suspected or known history of alcohol abuse or drug addiction within 2 years prior to the study vaccine dose that, in the opinion of the investigator, might interfere with protocol compliance.
- 13. Any other condition that, in the opinion of the investigator, would pose a health risk to the participant if enrolled or could interfere with evaluation of the study vaccine or interpretation of study results (including neurologic or psychiatric conditions likely to impair the quality of safety reporting).
- 14. Study team member or immediate family member of any study team member (inclusive of Sponsor, clinical research organization [CRO], and study site personnel involved in the conduct or planning of the study).
- 15. Participants with a history of myocarditis or pericarditis.
- 16. Respiratory symptoms in the past 3 days (ie, cough, sore throat, difficulty breathing).
- 17. Temperature of > 38°C within 24 hours of planned study vaccination (site measured or participant measured).
- 18. Blood pressure of \geq 160/100 mmHg.

5.2 Other Considerations for Eligibility Criteria

Participants meeting any of the following criteria may have planned study vaccination deferred for a later date, but these criteria are not exclusionary for study enrolment.

- Respiratory symptoms in the past 3 days (ie, cough, sore throat, difficulty breathing). Participant may be vaccinated once all symptoms have been resolved for > 3 days. Out-of-window study vaccination is allowed for this reason (see NOTE).
- Temperature of > 38°C within 24 hours of planned study vaccination (site measured or participant measured). Participant may be vaccinated once the fever has resolved and there has not been any temperature measured as being > 38°C for > 3 days without anti-pyrectics. Out-of-window study vaccination is allowed for this reason (see NOTE).

NOTE: PCR testing for SARS-CoV-2 is likely to be indicated for either of the above reasons or if COVID-19 is suspected based on other symptoms or for potential exposure to SARS-CoV-2 infection through close contacts or based on local epidemiology.

Any participant who is otherwise eligible with a blood pressure of ≥ 160/100 mmHg may be retested onsite several times over a 3-hour interval to achieve a lower blood pressure. If the blood pressure remains ≥ 160/100 mmHg, study vaccination should be deferred for a later date if, at that time, the participant's baseline blood pressure is found to be < 160/100 mmHg.

• Participants found to be SARS-CoV-2 positive during the study may be excluded from some analyses as per the statistical analysis plan (SAP) but will not be excluded from participation in the study.

6 STUDY CONDUCT

A complete description of study procedures for participants is provided in Section 6.1.2 and a SOE is provided in Table 1.

6.1 Study Summary

6.1.1 Scheduled Study Visits

All participants will follow the same treatment and assessment schedule and will remain on study for immunogenicity and safety data collection through Day 180, for a total study duration of up to 194 days (approximately 7 months).

During the study, participants will have the option of remote (home) visits for Visits 2 (Day 28), 4 (Day 90), Unscheduled (UNSCH) and EOS (Day 180). These home visits will be conducted by Illingworth Research Group who will act as an extension of the study trial sites. Illingworth Staff will be trained in the study and oversight will be provided by the PI they are assigned to support. Tasks conducted by the Illingworth Research team will include but not be limited to mobile research nursing, patient concierge, medical photography (if applicable) and any clinical research services/assessments as documented in the study protocol Schedule of Events and study plans for each visit conducted.

6.1.1.1 Scheduled Study Visits

Scheduled study visits will occur for Screening and at Days 0, 28, 56, 90 118, 146, and 180:

- Screening Period (Days -14 to 0).
- Day 0: Randomization and booster administration.
 - Screening and Day 0 procedures can be conducted on the same day when feasible.
- Day 28: Safety and immunogenicity follow-up for all participants.
- Day 56: Phone Visit Safety follow-up for all participants.
- Day 90: Safety and immunogenicity follow-up for all participants.
- Day 118: Phone Visit Safety follow-up for all participants.
- Day 146: Phone Visit Safety follow-up for all participants.
- Day 180: EOS visit for all participants. EOS procedures will be conducted via site visit when possible. These procedures should also be conducted for all participants upon early termination.

On vaccination Day 0, participants will remain in the clinic or under study staff observation for at least 15 minutes post-vaccination to be monitored for any immediate hypersensitivity and anaphylaxis reactions. Participants will utilize an electronic diary (eDiary) to record reactogenicity following vaccination. All participants will be asked to record reactogenicity on the day of vaccination and for an additional 6 days after vaccination. Should any reactogenicity event extend beyond 6 days after vaccination (toxicity grade ≥ 1), then it will be recorded using the Continuing Solicited AE form and followed to resolution per ICH guidelines for dataset capture. The toxicology grading scale implemented in the eDiary for the study is included in Appendix 2.

Qualitative PCR tests will be performed on all participants on study Day 0. Confirmed symptomatic cases of COVID-19 should be recorded as an AE, SAE, or COVID-19 relevant AESI as appropriate. Positive PCR swab results in asymptomatic participants should also be entered as an AE.

6.1.1.2 Unscheduled Study Visits

Unscheduled Visits may be conducted throughout the duration of the study either via in-person or by a Home Health Care provider as deemed necessary by the principal investigator. In many cases, they may be conducted by study personnel for safety follow-up for any participant experiencing a medical issue while on study. During an Unscheduled Visit, the principal investigator may elect to perform any of the assessments listed in the SOE (Table 1) including blood sample collection, physical assessments, or other optional testing for clinical evaluation of an AE. In situations where the unscheduled visit is not due to respiratory/non-respiratory symptoms consistent with suspected COVID-19, the visit may be done as an in-person clinical site visit or as a telehealth visit. If an in-person visit is done for non-COVID related symptoms, vital signs, physical examinations, and other procedures as needed may be done as requested by the Investigator.

Participants and their guardians will be instructed to monitor for respiratory/non-respiratory symptoms of COVID-19 during the study. In cases of suspected COVID-19 illness where the participant has not been evaluated at an offsite medical facility, they must contact the site within 3 days of symptom onset. If possible, the participant should have an in-person visit to help gather vital signs and do any necessary work up inclusive of physical examination. In cases where the participant has already been at an offsite facility, the site should endeavor to retrieve the visit notes. Only in situations where the participant cannot have an in-person visit should a telehealth visit be planned. Procedures for this visit are described in Section 6.1.2.8.2, and follow-up to confirm and assess the severity of the case of COVID-19 will be conducted at the next scheduled study visit.

6.1.1.3 COVID-19 Monitoring and Assessment of Severity

At each scheduled study visit, participants will be asked to report any PCR/rapid test confirmed cases of COVID-19 that occurred since last contact. Additional follow-up for any prior reported

cases of COVID-19 (ie, an unscheduled telehealth visit due to suspected COVID-19) will be conducted as well.

For all medically attended cases of COVID-19, an attempt will be made to obtain all medical records relevant to the COVID-19 healthcare visit and subsequent treatment in order to assess the severity of each case using the criteria provided in Appendix 3. Note, only the severity score should be recorded in the electronic case report form (eCRF).

All PCR/rapid test confirmed symptomatic cases of COVID-19 should also be recorded as an AE, SAE, or COVID-19 relevant AESI as appropriate.

Positive PCR swab results (performed in all participants at Day 0) in asymptomatic participants should also be entered as an AE.

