6.1.2.2 Day 0 – On-site Study Vaccination

The Screening and Day 0 Visits may be combined whenever feasible. If these visits are not combined, then the following procedures need to be performed and recorded for Day 0. Participant eligibility must be confirmed prior to vaccination.

Prior to study vaccination, all participants with confirmed eligibility will have the following procedures performed:

- Inclusion and exclusion criteria review via participant discussion and medical history review consistent with Section 4.1.1. Specific exclusions to study vaccination will be assessed before any study vaccination.
- Prior and concomitant medications, including recent and current medications to be reviewed to ensure eligibility criteria are fulfilled (see details in Section 7.4).
- Vital sign measurements, including respiratory rate, blood pressure, pulse rate, pulse oximetry, and temperature (oral or via forehead/ear reader). On study vaccination days, vital sign measurements will be collected once before study vaccination to ensure participant has no evidence of fever prior to study vaccination.
- Urine pregnancy test for participants of childbearing potential only. A urine pregnancy test will be performed prior to study vaccination. A positive urine pregnancy test at any time will result in the participant not receiving any further study vaccination.
- Symptom-directed (targeted) physical examination. Physical examination must be done prior to study vaccination.
- Nasal swab (anterior nares) collection for SARS-CoV-2 PCR testing
- Oral swab for SARS-CoV-2 mucosal IgA-mediated hACE2 receptor-binding inhibition assay
- Blood sampling for immunogenicity tests:
 - SARS-CoV-2 (ELISA for anti-S-protein serology).
 - SARS-CoV-2 serostatus (anti-N-protein serology).
 - SARS-CoV-2 NAb assay.
 - Human angiotensin converting enzyme-2 (hACE2) receptor-binding inhibition assay.
- Randomization/Enrollment

At the time of study vaccination, the following procedures will be conducted for all randomized participants:

- Alcohol swab cleansing of the injection sites for study vaccine administration
- Vaccination with study vaccine as an intramuscular (IM) injection.
- Monitoring for any immediate hypersensitivity and anaphylaxis reactions. Participants will remain in clinic for at least 15 minutes post-vaccination for safety monitoring.

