8.2 Documenting Adverse Events

At every study visit, participants will be asked to report any medically related changes in their well-being. They will also be asked if they have been hospitalized, had any accidents, used any new medications, or changed concomitant medication regimens (both prescription and OTC medications).

In addition to participant observations, AEs will be documented from any data collected on the AE page of the eCRF or other documents that are relevant to participant safety.

Care will be taken not to introduce bias when detecting AEs, MAAEs, and SAEs. Open ended and non-leading verbal questioning of the participant is the preferred method to enquire about AE occurrences. AESIs will be inquired about according to the specific diseases listed in Appendix 1.

When an AE/SAE occurs, it is the responsibility of the investigator to review all available documentation (eg, hospital progress notes, laboratory reports, and diagnostics reports) related to the event. The investigator will then record all relevant AE/SAE information in the eCRF.

It is not acceptable for the investigator to send photocopies of the participant's medical records in lieu of completion of the AE/SAE eCRF page. There may be instances when copies of medical records for certain cases are requested. In this case, all participant identifiers, with the exception of the participant number, will be redacted on the copies of the medical records before submission. The investigator will attempt to establish a diagnosis of the event based on signs, symptoms, and/or other clinical information. Whenever possible, the diagnosis (not the individual signs/symptoms) will be documented as the AE/SAE. The following variables will be recorded for each AE: verbatim/AE description and date for AE start and stop, severity, seriousness, causality, any other action taken, and the outcome. A new AE must be recorded if the severity of the AE changes.

Should an SAE have an outcome of death, the report should contain a comment regarding the co-involvement of progression of disease, if appropriate, and should assign main and contributory causes of death.

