8.2.2 Time Frame for Collection

All AEs captured following the procedures listed in the SOE (Section 1.1) will be recorded on the AE page of the eCRF.

Medical occurrences that begin prior to study vaccination will be recorded on the Medical History/Current Medical Conditions section of the eCRF and not in the AE section.

All unsolicited AEs of any severity will be collected from the time of study vaccination through 28 days after vaccination.

All MAAEs will be collected through 28 days after vaccination and only treatment-related MAAEs will be collected after Day 28 until EOS.

All AESIs will be collected from the time of study vaccination until EOS.

All SAEs will be collected from signing of informed consent until completion of the EOS.

All vaccine administration errors, AEs, SAEs, cases of multisystem inflammatory syndrome, and all cases of COVID19 following vaccination must be reported per applicable local regulatory reporting guidance for safety events that occur in participants during the study if they meet the regulatory reporting criteria.

At any time after completion of the EOS visit, if an investigator learns of an SAE that could reasonably be considered related to study vaccine, they should promptly notify the Sponsor.

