9.2.4 Per-Protocol Analysis Set

The Per-Protocol (PP) Analysis Set will be determined for each strain, serology assay and study visit. The PP Analysis set will include all participants who receive the full prescribed regimen of the study vaccine up to the visit according to protocol, have serology results for baseline and the time point analyzed, are PCR negative at baseline for SARS-CoV-2, and have no major protocol violations or an event (eg, COVID-19 infection) that are considered clinically relevant to impact immunogenicity response as determined prior to database lock.

Within the PP Analysis Set there are 3 subsets defined:

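### An asymptomatic positive on the pre-vaccination Day 0 PCR swab is sent to the AE page by Sections 6.1.1.1 and 6.1.1.3 and kept off it by Section 8.2.2

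*Protocol*

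**What the plan says.** **Where the result is to be recorded.** Section 6.1.1.3 names the Day 0 swab: "Positive PCR swab results (performed in all participants at Day 0) in asymptomatic participants should also be entered as an AE". Section 6.1.1.1 gives the same instruction in the paragraph that sets the Day 0 test for all participants: "Positive PCR swab results in asymptomatic participants should also be entered as an AE".

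**When the swab is taken.** Section 6.1.2.2 opens its list with "Prior to study vaccination, all participants with confirmed eligibility will have the following procedures performed", and the nasal PCR swab is on that list, ahead of randomization and the injection. Table 1 marks the Day 0 PCR cell with footnote 7, which also places it before the dose.

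**What is done with findings that predate the dose.** Under Section 8.2.2, findings which "begin prior to study vaccination will be recorded on the Medical History/Current Medical Conditions section of the eCRF and not in the AE section". The same section sets the collection window: "All unsolicited AEs of any severity will be collected from the time of study vaccination through 28 days after vaccination". The only collection before vaccination that it provides for is SAEs, from consent.

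**Whether such participants can be vaccinated and analysed.** Section 5.2 says that participants found SARS-CoV-2 positive during the study may be left out of some analyses "but will not be excluded from participation in the study". Section 9.2.4 limits the Per-Protocol set to those who "are PCR negative at baseline for SARS-CoV-2". The Safety Analysis Set (Section 9.2.3) has no such condition.

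**The concern.** A site with an asymptomatic positive on the Day 0 swab has two instructions for the same finding. One requires an AE entry. The other requires Medical History and rules out the AE section, so entering it in both places does not comply either.

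Two things are at stake. The first is consistency: the same baseline result may appear on different eCRF pages at different sites. The second is the unsolicited AE incidence through 28 days, which Section 3 lists as a primary safety endpoint. An infection already present before the dose could be counted there as if it arose after vaccination. The Protocol does not say how the entry is to be kept apart from post-vaccination AEs.

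**Working it through.** **Step 1: do the rules address the same finding?**

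| Question | Sections 6.1.1.1 and 6.1.1.3 | Section 8.2.2 |
|---|---|---|
| What is covered | Asymptomatic positive PCR; 6.1.1.3 names the Day 0 swab | Any medical occurrence beginning before vaccination |
| Destination | AE | Medical History, AE section excluded |
| Exception or cross-reference | None | None for PCR results |

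A positive on a sample drawn before the dose reflects an infection present before the dose, whenever the laboratory reports it. Section 8.1 defines an AE as an untoward medical occurrence. If the result counts as an AE under 6.1.1.3, it is therefore also a medical occurrence under 8.2.2. Both rules apply.

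**Step 2: can it arise in a vaccinated participant?** Yes. Section 9.2.4 has to remove baseline PCR positives from the Per-Protocol set, which presupposes that some receive vaccine. They stay in the Safety Analysis Set. Section 5.2 points the same way, although it speaks of positives found during the study and does not expressly mention the pre-dose result.

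**Step 3: would the planned summaries exclude it?** Section 9.3.1.2 ties unsolicited AE summaries to the Section 8.2.2 periods, which start at vaccination. That excludes a pre-dose event if timing relative to the dose is applied. However, Section 8.2 lists AE timing as dates: "The following variables will be recorded for each AE: verbatim/AE description and date for AE start and stop, severity, seriousness, causality". Section 8.2.3.1 counts events on or after the vaccination as treatment-emergent. Comparing dates alone, an entry dated Day 0 passes that test whether it preceded or followed the injection.

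**Step 4: size.** The Protocol states no figure on this point. From it: 400 participants, 200 per arm (Sections 4.1.2 and 9.1). Assumed: Day 0 asymptomatic positivity p of 0.5%, 1% or 2%, and a background share b of participants with another unsolicited AE of 5%, 10% or 20%.

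- Entries in total = 400 × p = 2, 4 or 8. Per arm = 200 × p = 1, 2 or 4.
- Chance of at least one case in the trial = 1 − (1 − p)^400 = 86.5%, 98.2% or 99.97%. The same formula with 200 reproduces the AE detection figures in Section 9.1: 1 − 0.95^200 = 99.996% (stated as greater than 99.9%) and 1 − 0.99^200 = 86.6%.
- Largest rise in incidence, if every entry is counted and none of these participants has another AE = p = 0.5, 1.0 or 2.0 percentage points.
- Rise allowing for other AEs = (1 − b) × p:

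| b | p = 0.5% | p = 1% | p = 2% |
|---|---|---|---|
| 5% | 0.48 | 0.95 | 1.90 |
| 10% | 0.45 | 0.90 | 1.80 |
| 20% | 0.40 | 0.80 | 1.60 |

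If the entries are filtered out, the rise is zero.

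**The case against.** The strongest reply is that the specific rule governs the general one. Section 6.1.1.3 names this swab, the instruction is repeated in Section 6.1.1.1 and in Table 1 footnote 2, and Section 8.2.2 itself begins by sending AEs captured through the schedule to the AE page. Repetition suggests intent. That is plausible, but the Protocol says so nowhere, and Section 8.2.2 excludes the AE section without qualification. If an exception is intended, it has to be written there.

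A second reply is that the collection window and the treatment-emergent definition already keep a pre-dose infection out of the endpoint, and that same-day derivations belong in the SAP. This limits the consequence and is accepted to that extent: with timing relative to the dose applied, the endpoint is unaffected. Day 0 PCR results are also tabulated under Section 9.4.1.2, so AE-page entries could be traced. None of this settles where a site should record the result, which is a conflict within the Protocol that an SAP does not resolve.

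Third, the size rests wholly on assumed rates, and the safety analyses are descriptive. Both are true, and they are why the point is rated as modest.

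**Conclusion.** The contradiction stands as written. Sections 6.1.1.1 and 6.1.1.3 cannot be followed together with Section 8.2.2 for an asymptomatic positive on the pre-dose Day 0 swab. The recording inconsistency follows from the wording alone and needs no assumption.

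The effect on the primary safety endpoint is conditional. It lies between zero, if pre-dose entries are filtered, and the assumed positivity itself, 0.5 to 2.0 percentage points here. It would inflate absolute incidence in both arms. It is not a systematic between-arm bias, because assignment is randomized and blinded. Per-Protocol immunogenicity is untouched, since baseline PCR positives are removed. This should be fixed, but it does not threaten the trial's conclusions.

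**What to change.** Reconcile Sections 6.1.1.1 and 6.1.1.3 with Section 8.2.2 in one of two ways:

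1. Record a positive on the pre-dose Day 0 swab as a baseline condition and report it with the Day 0 PCR tabulation already planned in Section 9.4.1.2; or
2. Keep the AE entry, declare it in Section 8.2.2 as an exception, and flag it as not treatment-emergent, so that it is left out of post-vaccination AE summaries and listed separately.

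Under either option, state that positives on swabs taken after vaccination remain AEs, as do Day 0 infections that worsen or become symptomatic after the dose. Table 1 footnote 2 carries the same sentence but is attached to unscheduled visits. It needs at most a clarification that it covers post-vaccination swabs.

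The cost is wording in three sections and one flag or derivation rule. No new data are needed.
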